The primary analysis will be based on the intent-to-treat (ITT) analysis set and will use multiple imputation to address missing values. The multiple imputation (MI) model will include sphere, cylinder, and axis measurements for both the investigational device and the gold standard device and baseline characteristics including age and gender. Analyses will be repeated in a per protocol analysis set that includes eyes with complete data.

Reliability (repeatability and reproducibility) of LFR-260 will be conducted in a subset of subjects for which measurements will be obtained twice in an office context. This analysis will be repeated in a remote context. Reliability will be evaluated using intraclass correlations for each of the continuous measurements, sphere, cylinder, and axis.

.

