# 2.3 Primary Endpoints

The primary effectiveness endpoint is to demonstrate that the LFR-260 is within 0.5D (+/-) in measuring sphere and cylinder results and within 10 degrees for axis results from the traditional phoropter. Precision testing will also be conducted to confirm repeatability and reproducibility of the LFR-260.

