#### 3.4 Inclusion criteria

Participants must fulfill all of the following criteria in order to be eligible for the study:

- 1. The participant or legal guardian is willing and able to understand, sign and date the Ethics committee approved study specific Informed Consent Form.
- 2. The participant is a male or female between the ages of 12 and 65 (inclusive).
- 3. The participant has a history of the following:
  - O No more than mild to moderate far-sightedness or near-sightedness (i.e. Spherical equivalent refraction (SER) between +10 to -15).
  - o an astigmatism of 2.5D or less.
  - o an anisometropia of 1.5D or less.
- 4. The participant is free of ocular and systemic abnormalities that might affect visual functions.

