#### 4.9.2 Precision Tests

# 1. Repeatability Testing (+1 hour post initial testing)

In a subset of 33 patients (11 per location), LFR-260 testing will be repeated by the same ECP to confirm the initial findings. One ECP per location will perform Repeatability Testing for a total of 3 ECPs included for this testing method.

- ECP will complete Refraction with LFR-260 one hour post initial testing
- Measure Best Corrected Visual Acuity
- Conclusion of Study: Study coordinator will complete the Study Exit Form, which will indicate the conclusion of subject participation in this study.

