# 2. Reproducibility Testing

In a separate subset of 33 patients (11 per location), LFR-260 testing will be reproduced by two separate ECP operators at each location for a total of 6 ECPs.

If the patient is randomized to Group I, the steps listed below will be completed at the beginning of the patient visit. If the patient is randomized to Group II, the steps listed below will be completed after the eye exam with use of the traditional phoropter.

- 1. ECP #1 will complete Refraction with LFR-260.
  - a. Best Corrected Visual Acuity will be measured.
- 2. ECP #1 will leave the room, and ECP #2 will complete Refraction with LFR-260.
  - a. Best Corrected Visual Acuity will be measured.

3. Conclusion of Study: Study coordinator will complete the Study Exit Form, which will indicate the conclusion of subject participation in this study.

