# 7.7 Other Planned Analyses

#### 7.7.1 Bland-Altman Agreement Analysis

Supporting analyses will evaluate the distribution of paired differences between LFR-260 and reference for the three dimensions (sphere, cylinder, and axis) using Bland-Altman agreement analysis. This will include determination of the standard deviation of paired differences, the 95% limits of agreement, and an evaluation of systematic bias. The Bland-Altman plot of paired differences versus the mean of measurements will be provided. The relationship between bias and the mean of measurements will characterized. The same analysis will be applied to the vector difference between LFR-260 measurements and the gold standard in terms of sphere and cylinder measurements. The vector differences is square root of (X1-Y1) + (X2-Y2) where the X1 and X2 are measurements of sphere and cylinder using the investigational devices and Y1 and Y2 are the same measurements using the gold standard.

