# 7.7.4 Reliability and Repeatability Analysis

Reliability of LFR-260 will be conducted in a subset of subjects for which measurements will be obtained twice in an office context. This analysis will be repeated in a remote context. Reliability will be evaluated using intraclass correlations for each of the continuous measurements, sphere, cylinder, and axis and for the vector measurement of sphere and cylinder.

For a subset of 33 subjects (66 eyes), the LFR-260 device will be measured again approximately 60 minutes after the initial assessment in order to measure the repeatability/accuracy of the device.

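### Repeat LFR-260 readings are to be summarised by an intraclass correlation of unstated form, with no precision estimate planned in dioptres or degrees

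*Combined protocol and SAP*

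**What the plan says.** Precision appears under section 2.3, Primary Endpoints: "Precision testing will also be conducted to confirm repeatability and reproducibility of the LFR-260".

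Section 4.9 sets out four separate subsets with a second LFR-260 reading:

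- repeatability, 33 subjects: "LFR-260 testing will be repeated by the same ECP to confirm the initial findings", about one hour later;
- reproducibility, 33 subjects: "LFR-260 testing will be reproduced by two separate ECP operators at each location";
- offsite, 21 subjects, and remote, 21 subjects: each compared with the initial LFR-260 result.

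The synopsis (Statistical Considerations) gives the analysis: "Reliability will be evaluated using intraclass correlations for each of the continuous measurements, sphere, cylinder, and axis". Section 7.7.4 repeats this and adds a vector, so that reliability is to be "evaluated using intraclass correlations for each of the continuous measurements, sphere, cylinder, and axis and for the vector measurement of sphere and cylinder", and says the analysis will also be done in a remote context. Neither place states the ICC model, whether it measures consistency or absolute agreement, whether it refers to a single or an average reading, a confidence interval, or an acceptance value. Section 4.9.3 (offsite) names no statistic.

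Section 7.7.1 does plan an SD of paired differences and 95% limits of agreement, but for another comparison: "Supporting analyses will evaluate the distribution of paired differences between LFR-260 and reference for the three dimensions". The vector there is likewise "applied to the vector difference between LFR-260 measurements and the gold standard in terms of sphere and cylinder measurements". The 0.5 D limit in 2.5.1 and 7.4 is also defined against the phoropter.

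**The concern.** An ICC is the share of total variance that lies between eyes. The same device error therefore looks better in a group of very different eyes and worse in a group of similar ones. Cylinder is limited by eligibility ("an astigmatism of 2.5D or less"), while spherical equivalent may range widely, so the sphere and cylinder ICCs need not be comparable even if the device is equally precise in both. A unitless figure also cannot be set against 0.5 D or a number of degrees, which is what a reader would need in order to judge whether repeatability and reproducibility have been shown.

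Two features add to this. First, the form is left open, and a consistency ICC ignores any constant shift between two readings. That matters most for offsite and remote use, because those readings are compared only with the initial LFR-260 reading and never enter the primary test. Second, axis is listed as an ordinary continuous measurement, although 1 and 180 degrees are adjacent, and no section mentions wrapping.

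At stake is whether the precision results can be interpreted, not the primary claim.

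**Working it through.** **Inputs.** From the documents: 33 + 33 + 21 + 21 = 108 subjects with a planned second LFR-260 reading; the 0.5 D agreement limit; cylinder up to 2.5 D. The documents give no between-eye SD (sb) or within-eye SD (sw), and no target or power for the precision analysis, so there is no plan figure to reproduce on this point. All SDs below are assumptions.

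**1. Same error, different ICC.** ICC = sb² / (sb² + sw²). Take sw = 0.30 D.

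- Repeatability coefficient: 1.96 × √2 × 0.30 = 0.83 D.
- Repeat pairs within 0.5 D: 2Φ(0.5 / (0.30 × √2)) − 1 = 76%, or about 85% if each reading is rounded to 0.25 D steps (simulation).

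| sb (D) | ICC |
|---|---|
| 0.5 | 0.25 / 0.34 = 0.74 |
| 0.72 (uniform over 0 to 2.5 D: 2.5/√12) | 0.85 |
| 1 | 1 / 1.09 = 0.92 |
| 2 | 0.98 |
| 3 | 0.99 |
| 4 | 0.99 |

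The first two rows are plausible for cylinder, the rest for sphere. The error in dioptres is the same throughout.

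**2. Constant shift of 0.5 D between office and remote, sw = 0.25 D.** The absolute-agreement ICC becomes sb² / (sb² + sw² + 0.5²/2). The consistency ICC keeps its no-shift value.

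| sb (D) | No shift, and consistency form with shift | Absolute agreement with shift |
|---|---|---|
| 0.5 | 0.80 | 0.57 |
| 0.72 | 0.89 | 0.74 |
| 1 | 0.94 | 0.84 |
| 3 | 0.993 | 0.980 |

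The mean paired difference shows such a shift directly. Its 95% half-width in 21 subjects is t × 0.25 × √2 / √n, which is 0.11 D if the 42 eyes are independent (n = 42) and 0.16 D if the two eyes of a subject carry no separate information (n = 21).

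**3. Axis.** Two million simulated pairs, whole degrees on a 1 to 180 scale, true within-eye SD 5 degrees, one-way ICC:

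| Where the axes lie | Unwrapped ICC | Within-eye SD, wrapped | Coefficient, wrapped |
|---|---|---|---|
| Uniform | 0.82 | 5.0 | 13.9 |
| Around 180 (SD 20) | 0.71 | 5.0 | 13.9 |
| Around 90 (SD 20) | 0.94 | 5.0 | 13.9 |

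If axis is analysed as listed, the ICC reflects where the axes lie. The wrapped figures recover the true error each time.

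**4. How far the primary test protects.** The stated power reproduces: with 216 eyes the exact test passes at 183 or more (183/216 = 0.847, lower bound 0.801), alpha is 0.046, and power at 0.90 is 99.5% against the stated 99%. For sphere and cylinder jointly, with 0.25 D steps, independent components and eyes, and axis left out:

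| LFR-260 sw (D) | Phoropter SD (D) | Joint agreement | Chance of passing |
|---|---|---|---|
| 0.50 | 0 | 61% | essentially nil |
| 0.30 | 0 | 92% | above 0.999 |
| 0.30 | 0.25 | 78% | about 1% |

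Axis is part of the endpoint. Adding a 5-degree axis error to the middle row (phoropter error-free, axis independent) lowers the chance of passing to about 0.96 if every eye has low astigmatism, 0.43 if 20% are moderate to high, and 0.04 if 40% are.

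**The case against.** The strongest reply is that this is a supporting analysis. No hypothesis, power statement or decision rule rests on it, and the within-eye SD and paired differences could be computed from the same data at reporting. Step 4 also shows that gross imprecision would very likely fail the primary test. All of that stands, and it limits the weight of the point. It does not remove it: the plan names a different statistic, and the primary test does not look at offsite or remote readings.

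Four stronger readings are tempting, and the documents do not support them.

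- A reader might infer that no ICC could reveal an office-to-remote shift. That holds for the consistency form, and nearly so for sphere when the spread is wide. An absolute-agreement cylinder ICC would fall visibly (0.80 to 0.57 at between-eye SD 0.5 D). Nothing in the documents suggests that a shift exists.
- A reader might infer that the vector ICC cannot be computed for repeat readings, because 7.7.1 defines the vector against the phoropter. Every subject is due a phoropter reading, so each LFR-260 reading can yield its own vector difference from it. The wording is ambiguous, and a definition is needed.
- A reader might take +10 to −15 as the spread of sphere. It is an eligibility range for spherical equivalent, described as mild to moderate, and says little about the enrolled spread. Hence the range of assumed SDs.
- A reader might infer that 2 and 178 degrees will be counted as 176 apart. The documents do not say how axis differences are formed; wrapping is unaddressed, not ruled out.

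**Conclusion.** The point holds as a cheap improvement that should be made. The ICC is the only statistic named for repeat readings in the office and remote contexts, its form is open, and no repeat-reading estimate in dioptres or degrees is planned. By itself it cannot place repeatability or reproducibility on the 0.5 D scale: one assumed error of 0.30 D gives anything from 0.74 to 0.99 as the between-eye SD goes from 0.5 to 4 D. For axis, one assumed error of 5 degrees gives 0.71 to 0.94 unless wrapping is handled.

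The real size is unknown, because every SD is assumed. No sample size or power figure changes, and the primary conclusion is largely protected. The main gains are a readable precision estimate and a direct view of any shift in offsite or remote use. Confidence is medium.

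**What to change.** Amend 7.7.4, and the synopsis to match:

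- **Same-ECP and two-ECP subsets, separately.** Report Sw = √(mean(d²)/2), where d is the difference between the two readings, so that a systematic ECP difference counts. Report 1.96 × √2 × Sw beside it, with subject-clustered 95% confidence intervals, for sphere and cylinder. Do the same for axis with differences wrapped to ±90 degrees, in eyes with non-zero cylinder on both readings.
- **Offsite and remote subsets.** Report the mean paired difference from the initial LFR-260 reading and 95% limits of agreement, with subject-clustered intervals and axis wrapped.
- **Percentage of repeat pairs within 0.5 D** for sphere and cylinder, noting that this limit was set for device against phoropter.
- **ICC.** Keep it for sphere and cylinder as descriptive, in single-measurement absolute-agreement form, with a stated model that respects ECPs nested in location. Drop the unwrapped axis ICC. State what the vector is for repeat readings, or drop its ICC.
- **Section 2.3.** Say that precision will be estimated, not confirmed, unless a precision criterion is stated in advance.

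The cost is SAP wording and a few tables, with no new data. The figures will look less flattering than a high ICC, and precision is modest. By the chi-square formula, the 95% interval for Sw with 33 subjects runs from 0.85 to 1.21 times the estimate if the 66 eyes are independent, and from 0.81 to 1.32 times with 33 degrees of freedom. For the SD behind the limits of agreement with 21 subjects, it runs from 0.82 to 1.28 times (41 degrees of freedom) or 0.77 to 1.44 times (20).

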# 8.0 Risk Analysis

The subjects in this study will be exposed to minimal increased potential risk. The majority of procedures in this study correspond to the standard of care procedures.

Trial-specific risks include the risks associated with investigational device (LFR-260) and the risks associated with trial-related investigations and data collection.

Clinical investigations performed in this trial include non-invasive diagnostic methods and interview questionnaires. These non-invasive diagnostics represent a minimal risk to the subject.

All adverse events regardless of whether they were investigational device- related will be reported and recorded according to current regulations. See Section 5 for more details.

# 9.0 Investigator Selection and Regulatory Assessment

# 9.1 Investigator Responsibilities

Investigators will be identified based on their qualifications to conduct the investigation. Evolution Optiks will further assess the qualifications of each Investigator and their staff by conducting a review of their CV, checking the status of the Investigator within the FDA Debarment List, discussing the availability of the correct subject population at the institution and through a review of the clinical space to ensure that the facility has adequate amenities to conduct the study according to the protocol. The final determination on an Investigator's participation will be made following review of the above criterion and completion of the Site Qualification/Pre-Study Visit.

# 9.2 Institutional Review Board Approval

Investigators will be responsible for obtaining the initial and continuing review approvals from the governing IRB for the institution at which the proposed clinical investigation is to be conducted. Written certification of approval, and any conditions of approval imposed by the IRB, will be submitted to Evolution Optiks prior to the site's participation in this investigation. Investigational supplies will not be shipped to participating sites until documentation of IRB approval has been provided to Evolution Optiks.

The Investigator and/or his staff is responsible for knowing and complying with any reporting requirements stipulated by their governing IRB.

# 9.3 Investigator's Agreement

Investigators will be advised of their responsibilities as Investigators in a clinical study. Investigators will also be advised regarding FDA regulations governing clinical studies under IDE regulations, and must abide by record keeping and reporting requirements. This information will be provided to the Investigators via the Investigator Agreement, which must be signed by the Investigator and returned to Evolution Optiks prior to study participation.

# 9.4 Regulatory documentation and Assessment of Facilities

As part of the study start-up process, the Investigator and their staff will be required to supply documentation of their qualifications to participate in the study as well as a Financial Disclosure Form. Prior to participation in the study, each Investigator is required to submit the following documentation to Evolution Optiks:

- A signed Investigator's Agreement
- A current signed and dated curriculum vitae (current within 2 years)
- A completed Financial Disclosure questionnaire

Written approval of the study protocol and associated Informed Consent Form / Assent from their governing IRB (This must be provided prior to Investigational product being sent to the site or any subjects being enrolled). The Investigator/site is also required to submit any information required as part of the approval/renewal process for their governing IRB. Reports of any protocol deviations, AEs and Lost-to-Follow-Up subjects should also be provided to the IRB according to their stated requirements.

The Site Qualification Visit or Pre-Study Visit enables the Monitor to review the following with the Investigator and his staff: clinical protocol, the Investigator's Brochure, the Investigational product(s) provided for the clinical study, Investigator responsibilities, data collection and reporting requirements.

Another purpose of this visit is for the monitor to assure that the Investigator:

- Has appropriate training, facilities, patient load, staff, time and willingness to comply with study requirements;
- Understands the requirement to submit the clinical protocol and Investigator's Brochure to the IRB for review and approval;
- Understands the requirement to maintain all study correspondence, study binders, case report forms and subject records on file; and
- Assumes responsibility for oversight of the investigation at his / her center

The monitor will complete a Pre-Study Visit Report to document all activities and topics reviewed during the visit as well as the site personnel present for the meeting. The report will also document any open action items identified as a result of the visit.

# 9.5 Informed Consent

Subjects expressing an interest in participating in the study will be provided a copy of the IRB approved Informed Consent Form /Assent (where applicable) for review. Any study-related questions posed by the potential subject will be answered by the Investigator or a qualified member of his/her study staff. Potential subjects willing to participate in the study will be required to sign and date the Informed Consent Form. Only those who meet all inclusion and exclusion criteria for the study may be enrolled. Execution of the Informed Consent Form must be obtained prior to initiating any study specific procedures. The signed original informed consent is to be maintained in the site records and the subject should be provided with a copy for their records. The entire Informed Consent process will be documented in the subject's medical record.

# 9.6 Subject Stipends

Subject stipend or reimbursement will be determined on an Investigator site basis. If subject payments are allowed and warranted, monetary amounts will be reviewed and approved by the governing IRB and documented within each site ICF.

# 9.7 Confidentiality of Data

Access to subject's records is restricted to the Clinical Investigators, clinical site support staff, and to Evolution Optiks or their designee. Investigators are to instruct their staff in the methods and importance of maintaining subject confidentiality. Case Report Forms will be stored in secure, access-controlled locations at both the clinical sites and Sponsor's locations. Traceability of all forms will be maintained. Subjects will be assigned a subject number by the EDC system at the time of screening. On all CRFs or other reporting forms, study subjects should be identified only by their assigned subject number and initials.

Study results reported by Evolution Optiks will be in aggregate form and individual identities will not be publicly disclosed. It is possible that regulatory authorities (i.e., FDA) may request detailed clinical information regarding specific subjects. In these situations, information will be provided to regulatory authorities by the assigned subject number and subject initials.

The investigator agrees that complete source documents for this study will need to be available to appropriately qualified personnel from Evolution Optiks (or their designated representative) or to country specific health authority inspectors after appropriate notification. The verification of Case Report Form data will be done by direct inspection of source documents (where permitted by law). Record review will be done in compliance with HIPAA and in a manner that protects subject confidentiality.

During the conduct of the study, Investigators must agree not to publicly disclose any study related information including the study design, results or conclusions of the investigation without prior consent of Evolution Optiks.

#### 9.8 Amendments to Protocol

While not expected, it is possible that Evolution Optiks may need to amend the clinical protocol (for example, at the request of the FDA, due to emergence of new information, etc.). In the event that this is needed, the protocol amendment will be reviewed and approved internally by the appropriate Evolution Optiks staff and the FDA. Once finalized, the amendment will be distributed to the participating Investigator sites. Protocol amendments must undergo IRB review and approval at each clinical site, but may undergo expedited review if minor changes are made in the protocol that does not alter subject risk. The written approval from the IRB for the amendment

should specifically refer to the Investigator, the protocol number and title, and reference any amendment numbers that are applicable.

#### 9.9 Protocol Adherence

It is the responsibility of each Investigator and Evolution Optiks to conduct this study in accordance with all aspects of the protocol, Institutional Review Board requirements, the Declaration of Helsinki, the Code of Federal Regulations 21 CFR Part 50- Protection of Human Subjects, 21 CFR Part 54- Financial Disclosure, 21 CFR Part 56- Institutional Review Boards, and 21 CFR 812- Subparts C, Responsibilities of Sponsors, Subpart D, IRB Review and Approval, Subpart E, Responsibilities of Investigators and International Organization for Standardization (ISO) 14155:2020 and general Good Clinical Practice (GCP).

In the event of protocol deviations, both Evolution Optiks and the IRB should be notified of the event via the Protocol Deviation Log as soon as possible. If necessary, corrective actions will be taken to ensure the subject's safety and the integrity of the clinical investigation including, but not limited to site or study termination.

